#### **14.2.4 Handling of Missing Data**

Every effort will be undertaken to ascertain completeness of data collection and limit premature discontinuations. All analyses will utilize only actual Subject data which is collected, and no imputation of missing data will be performed. However, partial dates in medication and adverse events may be imputed. The imputation principles will be described in the Statistical Analysis Plan.

### **15.0 Study Responsibilities**

#### **15.1 Sponsor Responsibilities**

The Sponsor is responsible for:

- manufacturing, packaging, and sterilizing Amplifi System components;
- preparing the Protocol and updating the Protocol, as needed, by providing proposed Protocol amendments to Investigators for submission to their local ECs for review and approval;
- selecting Investigators and Sites;
- maintaining an updated list of Investigators and Sites;
- selecting consultants for the Study;
- establishing regulatory standards consistent with local, regional, and national governmental regulations for Sites;
- providing financial support to Investigators and Sites, along with product liability and no-fault clinical study insurance;
- conducting Site initiation visits prior to Subject enrollment;
- providing Investigators with a signed Clinical Study Agreement (CSA), Investigator's Brochure, Protocol, all necessary CRFs, and all other Study-related documents necessary to conduct the Study;
- providing the Amplifi System, including all components necessary for Amplifi System placement, operation, use, and removal, to the Sites;
- providing Study-related accessory devices and materials necessary for Amplifi System placement, operation, use, and removal to the Sites for those Study-related accessory devices that are not reasonably available at the Site or the responsibility of the Investigator or Site to obtain or provide;
- providing instructions and training to Investigators and other Site Personnel

## Clinical Protocol FIH-3

Doc No: CLINP1837  
Revision: D  
DCO No: 25-009  
Effective Date: 02/06/25

involved in the Study on the proper placement, operation, use, care, and removal of the Amplifi System (including all components), and other Study-related accessory devices, either directly or through consultants;

- providing revisions to the ICF to Investigators, as needed;
- maintaining a Clinical Study Master File;
- granting or restricting the right of Site Personnel to access the Study EDC System along with Data Manager and database;
- providing Study monitoring and performing or overseeing all aspects of data quality assurance, including data collection, data auditing and monitoring at Sites, either directly or through consultants;
- reviewing data submitted by Investigators and Sites for accuracy and completion, and reviewing source documents to ensure accuracy and validity of all data recorded on CRFs, as needed;
- performing Site monitoring, either directly or through consultants;
- recommend corrective actions if serious or repeated deviations from the Protocol by a Site occur, or if a Site is not complying with the Investigator's Agreement, applicable local, regional, and national regulatory requirements, or any other conditions imposed by the local EC or the Sponsor;
- terminate an Investigator or Site's participation in the Study if serious or repeated deviations from the Protocol by an Investigator continue to occur, even after corrective action recommendations and apparently adequate responses and actions, or if Sponsor determines that there is an unacceptable risk to Subject safety if an Investigator were to continue to enroll Subjects or participate in the Study;
- reviewing all reports of known or suspected AEs, SAEs, SADEs, and USADEs;
- reviewing all reports of known or suspected Amplifi System deficiencies, malfunctions, and unplanned stoppages;
- communicating information and reporting all SAEs, SADEs, and USADEs to the appropriate regulatory agencies and bodies in accordance with relevant local, regional, and national regulatory requirements;
- completing the Interim Analysis;
- completing the Final Analysis; and
- performing Study termination visits prior to Study termination; and
- reviewing all publications and presentations related to the Study.

### 15.2 Investigator Responsibilities

The Investigator is responsible for:

- providing Sponsor with current curriculum vitae;
- signing the Protocol and the Investigator's Agreement in the appropriate locations;
- receiving adequate training on the design, function, storage, placement, use, operation, maintenance, care, cleaning, monitoring, interaction with, removal, and disposal of the Amplifi System and its components before enrolling Subjects;
- understanding the Protocol, carrying out the Study in accordance with the Protocol, and

## Clinical Protocol

### FIH-3

Doc No: CLINP1837  
Revision: D  
DCO No: 25-009  
Effective Date: 02/06/25

- ensuring the Protocol is being properly followed during the Study;
- obtaining local EC approval of the Study before enrolling Subjects;
- keeping the Sponsor informed of all their local EC actions concerning the Study;
- determining if a patient meets all the inclusion criteria and none of the exclusion criteria prior to enrollment;
- obtaining informed consent from Subjects;
- updating and revising the ICF and re-consenting Subjects, as necessary;
- determining if patients are indicated for creation of a wrist or distal forearm radiocephalic AVF based on their standard practice, prior to enrolling patients as Subjects;
- determining if a Subject's internal jugular vein is suitable for Amplifi Inflow Catheter insertion;
- establishing an Amplifi System treatment time for each Subject prior to initiating treatment;
- ensuring Site Personnel carrying out Study activities have appropriate experience and training;
- performing all tests, assessments, procedures, interventions, and surgeries that are specified in the Protocol to be performed by Investigator, including:
  - placing of the Amplifi System;
  - initiating Amplifi System treatment;
  - obtaining contrast venography during Amplifi System placement, evaluation, and removal procedures;
  - obtaining outflow vein measurements using B-mode ultrasonography during Amplifi System treatment, as needed;
  - removing the Amplifi System; and
  - creating the Study AVF,
  - overseeing the performance of other tests, assessments, procedures, and surgeries specified in the Protocol or needed by Subjects;
- providing patient care for Subjects in accordance with the requirements and guidelines of Sites, federal, state, and local regulatory bodies and agencies, and reasonable standards of care;
- providing or overseeing instruction and training on the monitoring and care of the Amplifi System to Subjects and their homecare providers, as needed;
- ensuring that Study observations and findings are recorded correctly and completely in CRFs;
- maintaining accurate, complete, and current Study documents as specified in **Section 10.7** and ensuring the information recorded and submitted to the Sponsor is representative of the Subject's record and other supporting documentation;
- providing Sponsor with the Study documents and records necessary for a complete review of the work related to the Study at the Site by Investigator;
- meeting all Study reporting obligations, including:
  - reporting actual or suspected Amplifi System deficiencies, malfunctions, or

- unplanned stoppages to Sponsor, as specified in **Section 12.10 Reporting**;
- reporting actual or suspected AEs, SAEs, SADEs, and USADEs to Sponsor, as specified in **Section 12.10 Reporting** and submitting accurate, complete, and timely adverse event reports to Sponsor; and
- submitting all other reports to the Sponsor that are required,
- grading adverse events using the scale summarized in **Section 12.2 Classification of Adverse Events**;
- determining whether, in the opinion of the Investigator, an adverse event is related to the Amplifi System or Study procedures or surgeries using the criteria summarized in **Section 12.2 Classification of Adverse Events**;
- determining whether, in the opinion of the Investigator, an Amplifi System-related complication is an Amplifi System-related major complication;
- following all known and suspected AEs, ADEs, SADEs, and USADEs until they have resolved, have a stable level of sequelae, or, in the Investigator's opinion, are no longer clinically relevant;
- understanding and accepting the obligations of continuing review by their local EC while conducting the Study, including notifying their local EC of any changes to the Protocol per their local EC requirements, and submitting required reports to their local EC;
- reporting deviations from the Protocol to the Sponsor, as specified in **Section 10.9 Protocol Deviations and Investigator and Site Suspension and Termination**;
- notifying their local EC of Protocol deviations in accordance with their local EC requirements;
- reporting known and suspected AEs, SAEs, SADEs, and USADEs to their local EC in accordance with their local EC requirements;
- understanding and complying with all applicable local, regional, and national regulatory requirements while conducting the Study;
- communicating SAE, SADE, and USADE information and reporting all SAEs, SADEs, and USADEs to the appropriate regulatory agencies and bodies in accordance with relevant local, regional, and national regulatory requirements;
- recording the reason for withdrawal in source documentation and on the appropriate CRF for Subjects that withdraw from the Study;
- understanding the requirements for Amplifi System device and component accountability;
- returning all unused Amplifi System components to Sponsor at the end of the Study or at the end of the participation of a Site in the Study;
- submitting a Study summary to the Sponsor and their local EC promptly after the completion of the Study or at the end of the participation of a Site in the Study;
- providing data for publications and presentations related to the study, as needed by Sponsor and other Investigators; and
- reviewing all publications and presentations related to the study, as needed by Sponsor and other Investigators.

### **15.3 Site Personnel Responsibilities**

## Clinical Protocol FIH-3

Doc No: CLINP1837  
Revision: D  
DCO No: 25-009  
Effective Date: 02/06/25

Site Personnel are responsible for:

- understanding the Protocol, carrying out the Study in accordance with the Protocol, and ensuring the Protocol is being properly followed during the Study;
- receiving adequate training on the design, function, storage, placement, use, operation, maintenance, care, cleaning, monitoring, interaction with, removal, and disposal of the Amplifi System and its components before participating in the care of Subjects;
- reviewing the Amplifi System IFU prior to participating in the storage, placement, use, operation, maintenance, care, cleaning, monitoring, interaction with, removal, and disposal of the Amplifi System and its components;
- providing instruction and training on the monitoring and care of the Amplifi System to Subjects and their homecare providers, as needed.
- meeting all Study reporting obligations, including:
  - reporting deviations from the Protocol to the Sponsor, as specified in **Section 10.9 Protocol Deviations and Investigator and Site Suspension and Termination**;
  - reporting actual or suspected SAEs, SADEs, and USADEs to Investigators, as specified in **Section 12.10 Reporting**;
  - reporting actual or suspected Amplifi System deficiencies, malfunctions, or unplanned stoppages to Investigators, as specified in **Section 12.10 Reporting**; and
  - submitting all other reports to the Sponsor that are required; and
- providing Study documents and records necessary for a complete review of the work related to the Study at the Site to Sponsor.

### 15.4 Site Responsibilities

Sites are responsible for:

- providing and maintaining adequate resources to the Investigator at the Site to conduct the Study in accordance with the Protocol;
- ensuring Site Personnel carrying out Study activities have appropriate experience and training;
- maintaining copies of all submissions to, and correspondence with, local ECs (including approvals) and other regulatory bodies or agencies (if any) on file at the Site;
- making Site available for a Site initiation visit prior to Subject enrollment;
- keeping Amplifi System components used in the Study stored in a secure area separate from other medical devices in a location with restricted access that is accessible only by authorized Site Personnel and maintain associated Amplifi System storage and accountability logs and records;
- using a Subject's Study identification codes on all Study-related materials and de-identifying data prior to submission to Sponsor.
- providing Subjects treated with the Amplifi System with 24 hours per day, 7 days per week access for consultation with an Investigator or trained Site Personnel to answer questions from Subjects and their caregivers related to the Amplifi System, assist Subjects in responding to Amplifi System alarms and for other unanticipated events or

- Subject concerns, and assisting in the scheduling of care for Subjects;
- maintaining Study documents and original documentation supporting the data recorded on CRFs at the Sites;
  - keeping original and updated signed ICFs for each Subject on file and available for inspection by Sponsor or its designees;
  - retaining Study records in accordance with their local EC requirements;
  - notifying their local ECs of Protocol deviations in accordance with their local EC requirements; and
  - upon request, providing to the Sponsor the necessary Study documents and records for a thorough review of the work related to the Study at the Site.

## **15.5 Independent Safety Board (ISB) and Medical Monitor (MM) Responsibilities**

The ISB shall consist of a minimum of 3 physicians who are experts in the fields of nephrology, vascular access surgery, and diagnostic and interventional radiology, who are not participating in the study, and who do not have any investment with the study Sponsor. Membership will be restricted to individuals who have no significant conflict of interest (COI) as described in the COI section. One member of the ISB shall serve as the Chair and one member shall serve as the Medical Monitor with an adjudication role but no voting role.

## **16.0 Risks and Benefits**

### **16.1 Background**

The Amplifi System has not been authorized for commercial distribution in the US by the FDA nor has it been authorized for commercial distribution by any other regulatory agency. Bench, laboratory, and animal testing has been performed on the Amplifi System in studies and a first-in-human clinical study has been completed, as summarized in this Protocol and in the Amplifi System Investigator's Brochure.

A risk analysis has been conducted. The risks associated with the placement, operation, use, and removal of the Amplifi System have been identified by performing a Failure Mode and Effect Analysis (FMEA) and Risk Analysis, as a risk/benefit assessment. Risks have been proven, minimized, or eliminated through appropriate design control, confirmed by bench, laboratory, and animal testing, and a first-in-human clinical study.

The Amplifi System shares many similarities with extracorporeal blood pump systems and catheters that convey blood from patients to pumps and to return blood from pumps to patients, including devices for hemodialysis (including home hemodialysis), extracorporeal membrane oxygenation (ECMO), extracorporeal circulatory support, including the following similarities:

- Amplifi System catheters, hemodialysis catheters, ECMO catheters, and extracorporeal circulatory support catheters are designed for insertion into an internal jugular vein with tip placement in the superior vena cava or right atrium;
- Amplifi System catheters, hemodialysis catheters, ECMO catheters, and extracorporeal

## Clinical Protocol FIH-3

Doc No: CLINP1837  
Revision: D  
DCO No: 25-009  
Effective Date: 02/06/25

- circulatory support catheters are designed to connect to extracorporeal blood pumps;
- the Amplifi System pump and catheters and some hemodialysis pumps and catheters, ECMO pumps and catheters; and extracorporeal circulatory support pumps and catheters are designed to remove and return patient's blood at similar flow rates;
- Amplifi System catheters, hemodialysis catheters, and ECMO catheters are intended for chronic use, with hemodialysis catheters routinely used for many months and even years in some cases; and
- Patients and caregivers can be trained to perform Amplifi System and hemodialysis treatment in an inpatient setting.

The risk profile of the Amplifi System is similar or lower than hemodialysis blood pumps and catheters (including those for home use), and ECMO and extracorporeal circulatory support pumps and catheters.

### 16.2 Review of Literature

Sponsor reviewed the published safety data associated with hemodialysis blood pumps and catheters, ECMO blood pumps and catheters, and circulatory support blood pumps and catheters. The review of this data is summarized in **Attachment 2: Literature Review for Safety**. The potential safety events reported in these devices used in a similar patient population described in **Attachment 2: Literature Review for Safety** are comparable to the potential safety events identified in the risk analysis for the Amplifi System.

### 16.3 Benefit Analysis

Enlarging the cephalic vein in hemodialysis patients prior to forearm radiocephalic AVF through Amplifi System treatment has the potential to:

- improve suitability for forearm AVF creation;
- increase the rate of forearm AVF maturation;
- reduce the time required for forearm AVF maturation and use;
- identify pre-existing disease and potentially problematic side branches in veins of the upper extremity prior to AVF creation;
- reduce catheter contact time and catheter-related bloodstream infections;
- provide for easier AVF cannulation;
- provide higher hemodialysis session blood flows, which could allow for shorter hemodialysis sessions and more efficient hemodialysis
- reduce complications and hospitalization rates related to vascular access;
- reduce the number of procedures and surgeries needed to regain or maintain vascular access;
- increase wrist and distal forearm radiocephalic AVF prevalence;
- reduce the overall cost of care; and
- reduce mortality risk.

## Clinical Protocol FIH-3

Doc No: CLINP1837  
Revision: D  
DCO No: 25-009  
Effective Date: 02/06/25

The risk benefit ratio for using the Amplifi System in the Study has been deemed appropriate for an Investigational Device Exempt clinical study and the risk to Subjects has been appropriately mitigated to protect their safety.

### 16.4 Risk/Benefit Analysis

The risks associated with the placement, operation, use, and removal of the Amplifi System have been identified, confirmed by bench, laboratory, and animal testing and a first-in-human clinical study, are well understood, and have been eliminated or minimized through appropriate design control. Based on bench, laboratory, and animal testing of the Amplifi System, and results of a first-in-human clinical study, the potential benefits to Subjects from creation of a distal forearm radiocephalic AVF with an enlarged cephalic vein that matures rapidly and fully is clear and balances the risk. A literature review shows the risk/benefit profile for Subjects receiving Amplifi System treatment in the Study is similar to patients currently receiving treatment with widely used blood pump systems, including home hemodialysis, ECMO, and extracorporeal circulatory devices, providing additional support for the assessment that the risk/benefit profile for the use of the Amplifi System in the Study is acceptable.

### 16.5 Risk Mitigation

The Study has been designed to protect the safety and well-being of all Subjects. During the Study, potential risks will be controlled and mitigated through extensive training of Investigators and other Site Personnel, compliance with the Protocol, monitoring of Subjects during the Amplifi System treatment period, and ensuring the availability of additional treatment and support measures for Subjects, as needed.

## 17.0 Miscellaneous

### 17.1 Publication Policy

The first publication or presentation of the clinical results of the Study shall be made as a joint, multi-center publication or presentation by the Investigators at Sites that enrolled Subjects and contributed data and analyses, participated in the review of the data, and contributed to the preparation of the publication or presentation. All publications and presentations of the clinical results of the Study will be reviewed by all Investigators and approved by the Sponsor, and in accordance with the Site-specific CSAs.

## Appendix 1: Definitions

- *Abandonment of Study AVF* is defined as the discontinuation of the clinical use of Study AVF because it is no longer functional and considered not to be salvageable, including the discontinuation of the clinical use of Study AVF because it can no longer be used for prescribed hemodialysis, because it is unable to provide adequate blood flow, or because it is deemed unsafe for the patient, and the associated problem(s) cannot be corrected by any medical, procedural, or surgical intervention.
- *Amplifi System and AVF local infection* is defined as: 1) the presence of purulent discharge from the Inflow Catheter skin exit site, the Distal Outflow Catheter skin exit site, or the Study AVF skin incision; or 2) the presence of serous discharge from the Inflow Catheter skin exit site, the Distal Outflow Catheter skin exit site, or the Study AVF skin incision with erythema, induration, or tenderness and a positive culture of the serous discharge.
- *Amplifi System component replacement* is defined as the replacement of one or more components of the Amplifi System during the Amplifi System treatment period, not including replacement or addition of Access Port caps, suture anchoring tools, a Patient Vest, or Patient Vest components.
- *Amplifi System-related major complication* is defined as:
  - Amplifi System-related death;
  - Amplifi System-related major bleeding, major pneumothorax, major air embolism, major thrombosis, major thromboembolism, major hemolysis, or major thrombocytopenia; local infection
  - Amplifi System-related re-hospitalization or prolonged hospitalization;
  - Amplifi System-related major surgery or major interventional procedure; or
  - any Amplifi System-related complication determined to be an Amplifi System-related major complication by both an Investigator and the CEC.
- *Amplifi System-related major bleeding* is defined as:
  - overt bleeding plus a drop in hemoglobin of 3 to 5 g/dL wherein the hemoglobin drop is related to the bleeding;
  - transfusion for overt bleeding;
  - bleeding requiring an interventional procedure or surgery for control (not including the placement or removal of skin sutures or pressure dressings);
  - the administration of intravenous vasoactive agents for overt bleeding; or
  - probable or definite fatal bleeding.
- *Amplifi System-related major pneumothorax* is defined as the introduction of air in the cavity between the lungs and the chest wall during the placement, operation, use, or removal of the Amplifi System that is not due to a cause other than the placement, operation, use, or removal of the Amplifi System, wherein the pneumothorax is documented by imaging and a chest tube is placed.
- *Amplifi System-related major air embolism* is defined as the entry of air into the vascular

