#### Safety Measures

- **Rate of Occurrence of Major Device-Related Adverse Events (MDRAE)\* defined as:** [Timeframe: from device implantation and up to 30 days from device removal and AVF creation]
  - Amplifi System-related death;
  - Amplifi System-related major bleeding, major pneumothorax, major air

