## Clinical Protocol FIH-3

Doc No: CLINP1837  
Revision: D  
DCO No: 25-009  
Effective Date: 02/06/25

embolism, major thrombosis, major thromboembolism, major hemolysis, or major thrombocytopenia; local infection

- Amplifi System-related re-hospitalization or prolonged hospitalization;
- Amplifi System-related major surgery or major interventional procedure; or
- any Amplifi System-related complication determined to be an Amplifi System-related major complication by both an Investigator and the Medical Monitor.

\*Detailed definition of Major Device-Related Adverse Events is described in **Attachment 1: Definitions**

- **Rate of Occurrence of Cannulation-related Complications** [Timeframe: from AVF creation through end of follow-up period]

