### 12.2.4 Serious Device Adverse Effects

For SAEs or suspected SAEs that are categorized by an Investigator as definitely, possibly, or probably related to the Amplifi System, the Medical Monitor will adjudicate whether the SAE or suspected SAEs is a SADE.

Investigators will review all reports of Amplifi System deficiencies, malfunctions, or unplanned stoppages and determine if an SAE or suspected SAE occurred. If an Investigator determines that an SAE or suspected SAE occurred, they will document the SAE or suspected SAE on the appropriate CRF. The Investigator will also document, in their opinion, the likelihood the SAE was related to the Amplifi System using the relational criteria summarized in **Section 12.2 Classification of Adverse Events** and the Medical Monitor will adjudicate with PI whether the SAE or suspected SAE is a SADE.

Investigators will follow all SADEs and suspected SADEs until they have resolved, have a stable level of sequelae, or, in the Investigator's opinion, are no longer clinically relevant.

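### The catch-all limb of the major device-related adverse event composite names two different adjudicators, and both versions need the Investigator to agree

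*Protocol*

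**What the plan says.** The MDRAE rate is the first safety measure listed in Section 4.5 and in the synopsis. Both places close the list of qualifying events with a catch-all: "any Amplifi System-related complication determined to be an Amplifi System-related major complication by both an Investigator and the Medical Monitor". A footnote in Section 4.5 adds "Detailed definition of Major Device-Related Adverse Events is described in" the definitions attachment, which in this document is Appendix 1.

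Appendix 1 has no entry under the MDRAE name. Its entry for a system-related major complication carries essentially the same limbs, but its last one reads: "any Amplifi System-related complication determined to be an Amplifi System-related major complication by both an Investigator and the CEC".

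Three other sections bear on who decides:

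- Section 15.5 sets up an Independent Safety Board of physicians "who are not participating in the study, and who do not have any investment with the study Sponsor" and provides that "one member shall serve as the Medical Monitor with an adjudication role but no voting role".
- Section 15.2 lists among the Investigator's duties "determining whether, in the opinion of the Investigator, an Amplifi System-related complication is an Amplifi System-related major complication".
- Section 12.2.3, in the definition of a serious adverse event, has its own catch-all that also needs both the Investigator and the Medical Monitor.

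**The concern.** There are two problems in the same limb.

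First, the place a coder is sent for the detailed definition names a different decision-maker from the place that sends them. The supplied text gives the CEC no members, role or procedure.

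Second, both versions require agreement, and neither says what happens when the two parties differ. The Investigator places the device, removes it and creates the fistula (Section 15.2). The Medical Monitor belongs to a board chosen for its independence. If the Investigator says an event is not major and the Medical Monitor says it is, the event stays out of the MDRAE rate. Compared with counting on the independent reviewer's decision alone, this rule can only lower the count.

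The study's safety objective is to confirm that major events are in an acceptable range. With at most ten subjects and no comparator arm, the classification of a single event is visible in the result.

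**Working it through.** The protocol gives no event rate, power or threshold for this measure, so there is no figure of its own to reproduce. The check is mainly a comparison of text, with a short calculation for scale.

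**Who must agree that a catch-all event is major**

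- Synopsis, safety measures: an Investigator and the Medical Monitor.
- Section 4.5, safety measures: an Investigator and the Medical Monitor.
- Appendix 1, major complication: an Investigator and the CEC.

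**Is a CEC set up anywhere?** It is not in the abbreviation list or the table of contents, and no supplied section describes it. The Central EC in Sections 10.8 and 12.10 is an ethics committee with approval and reporting functions. The adjudicator described in Sections 12.2.2, 12.2.4, 12.2.5, 12.3 and 15.5 is the Medical Monitor.

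**Which events depend on this limb?** Only those that meet no other limb. System-related death, local infection, re-hospitalization and prolonged hospitalization count without any agreement rule. Other limbs are narrower: major thrombosis in Appendix 1 leaves out a thrombectomy done during fistula creation, although Section 7.5 foresees thrombus being dealt with at that point after a pump stoppage. Section 12.2.6 lists vascular injury, catheter dislodgement and component fracture as possible events, and none is a limb by name. Where such an event neither lengthens the stay nor meets another limb, the catch-all is its only way into the rate.

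**Direction of the rule.** Let p_I and p_M be the chances that the Investigator and the Medical Monitor call a truly major event major. Whatever the dependence between them, P(both say yes) ≤ p_M. If their judgements are independent, P(both) = p_I × p_M. The documents give neither value, so the following ranges are assumptions:

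- p_I from 0.5 to 1.0 and p_M from 0.7 to 1.0.
- Both must agree: 0.5 × 0.7 = 0.35 up to 1.0 × 1.0 = 1.00.
- Medical Monitor alone: 0.70 to 1.00.

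**Size of one event at n = 10** (the maximum, from the synopsis and Section 4.3), with exact Clopper-Pearson 95% limits:

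- 0/10: rate 0%; lower limit 0; upper limit 1 − 0.025^(1/10) = 0.3085, or 30.8%.
- 1/10: rate 10%; lower limit 1 − 0.975^(1/10) = 0.0025, or 0.3%; upper limit is the p solving (1 − p)^10 + 10p(1 − p)^9 = 0.025, which is 0.445, or 44.5%.

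One event left out therefore moves the rate by 1/10 = 10 percentage points, and by more if fewer than ten are enrolled.

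**The case against.** The best defence is that this is a slip in one appendix line. The synopsis and Section 4.5 agree with each other and name the Medical Monitor, whose adjudication role runs through the protocol. Requiring two physicians to agree on a discretionary addition to a defined list is a legitimate design choice, used again in Section 12.2.3. The veto also runs both ways, since the Medical Monitor can block the Investigator. The study is unpowered and descriptive, and no success threshold is set for this rate.

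Much of that stands, and it rules out several stronger readings that a reader might infer:

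- *That the catch-all can never be met.* This takes the Appendix 1 line alone. Read with Section 4.5, the limb can be met.
- *That a CEC does not exist.* The documents show only that the supplied protocol does not set one up. The adjudication charter cited in Section 12.10 is not at hand. Absence from the abbreviation list proves little, because ISB and MDRAE are missing from it too.
- *That the catch-all is the general route for serious device harm.* Several limbs have no narrow threshold, and subjects stay in hospital until device removal (Section 7.0), so much serious harm would count as death, readmission or a longer stay.
- *That excluded events disappear.* Section 14.2.3 tabulates adverse events and device effects, with severity and causal relation.
- *That Section 12.2.4 shows the same veto.* Its second paragraph says "the Medical Monitor will adjudicate with PI whether the SAE or suspected SAE is a SADE", while its first has the Medical Monitor adjudicate with no mention of the PI. That concerns serious adverse device effect status, not the MDRAE rate, and need not mean that the PI must concur.

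The defence does not remove the conflict between Section 4.5 and the appendix it cites, or the lack of a rule for disagreement. The general tables keep an event visible but do not put it back into the MDRAE rate.

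**Conclusion.** The concern holds in a limited form. The catch-all limb names two different adjudicators, one of them not set up in the supplied protocol. Both versions let the Investigator's refusal keep out of the MDRAE rate an event that the independent reviewer judges major. The effect is confined to complications outside the listed limbs and, relative to the independent decision alone, can run only toward a lower rate.

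For one such event among 10 subjects, the report would show 0/10 (0 to 30.8%) instead of 1/10 (0.3 to 44.5%). This is the size of a single disagreement, not an expected bias, because the frequency of disagreement is unknown.

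The conclusion rests on reading the Appendix 1 major complication entry as the definition Section 4.5 refers to, which the cross-reference and the near-identical limbs support. It also takes the agreement rule literally. The wording asks for an Investigator without saying which one, so with several Investigators the agreement of any one could suffice.

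**What to change.** - In the synopsis, Section 4.5 and Appendix 1, name the Medical Monitor as adjudicator of the catch-all limb in identical words, and remove the CEC.
- State that the Medical Monitor's classification is the one analysed for the MDRAE rate. Keep the Investigator's opinion (Section 15.2) as a recorded item, but do not require it to agree.
- Align the parallel two-party rule in the serious adverse event definition in Section 12.2.3.
- As a separate consistency point, reconcile the two paragraphs of Section 12.2.4 on whether the Medical Monitor adjudicates serious adverse device effect status alone or with the PI.

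The cost is a wording amendment. No new staff are needed, since the Medical Monitor already adjudicates. The reported rate may be slightly less favourable. The change does not remove the Investigator's earlier judgement of relatedness, which under Sections 12.2.2 and 12.2.4 decides which events go to the Medical Monitor for device-effect adjudication.
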